9.3 Definition of Populations

For this study, we will utilize a per-protocol analysis dataset. We will only consider randomized participants who completed the Sham SCS treatment along with at least one other active (i.e., burst, tonic 1 kHz, tonic 50 Hz) SCS treatment along with the associated outcome measures for each treatment.

9.4 Interim Analyses and Stopping Rules

Planned interim analyses: There are no planned interim analyses.

Safety analyses: In this post-approval mechanistic study, we will not evaluate a formal safety endpoint. We will code adverse events (AEs) according to the Medical Dictionary for Regulatory Activities (MedDRA) preferred terms. We will calculate AEs once for a given participant. We will present AEs with regards to severity, frequency, relationship, and expectedness. We will present serious AEs leading to premature discontinuation from the study in a table. We will collect and summarize adverse events, including the proportion of participants who experience at least one AE and the number of AEs per participant. We will also determine if the AE rates for this study were consistent with pre-study assumptions derived from AE rates in previously published studies. Potential differences in the AE rates between this study and prior studies could have significant implications for interpreting the results of this study.

This study will be stopped prior to its completion if: (1) the intervention is associated with adverse effects that call into question the safety of the intervention; (2) difficulty in study recruitment or retention; (3) any new information becomes available during the trial that necessitates stopping the trial; or (4) other situations occur that might warrant stopping the trial.

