All AEs including local and systemic reactions not meeting the criteria for SAEs will be captured on the appropriate case report form (CRF). Information to be collected includes event description, time of onset, clinician's assessment of severity, relationship to study product (assessed only by those with the training and authority to make a diagnosis), and time of resolution/stabilization of the event. All AEs occurring while on study will be documented appropriately regardless of relationship. All AEs will be followed to adequate resolution.

Any medical condition that is present at the time that the participant is screened will be considered as baseline and not reported as an AE. However, if the study participant's condition deteriorates at any time during the study, it will be recorded as an AE.

Changes in the severity of an AE will be documented to allow an assessment of the duration of the event at each level of severity to be performed. AEs characterized as intermittent require documentation of onset and duration of each episode.

Reporting adverse events: We will report SAEs to the IRBMED per the IRBMED Standard AE Reporting Plan at <https://az.research.umich.edu/file/864>. If the SAEs are not related to the study, we will report them at the study continuing review. If the SAEs are related to the study, we will report them within seven days or sooner to the IRB. We will also report AEs and SAEs to the Principal Investigator (PI). If there is any evidence of a pattern of unanticipated AEs (regardless of causality), or SAE, we will immediately have an independent third party review these data. Based on the conclusions of this third party, the PI will either terminate the study or convene a Data Safety and Monitoring Board (DSMB) to make recommendations.

Reporting events to participants: We will inform both the subject and the subject's physician in the event that a potentially significant, unexpected disease or condition is identified incidental to a study treatment or procedure.

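### Section 9.4 counts AEs once per participant and plans no summary by treatment at onset, so this four-treatment crossover would pool sham with active stimulation in its safety tables

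*Combined protocol and SAP*

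**What the plan says.** The safety paragraph of section 9.4 states that "we will not evaluate a formal safety endpoint". After MedDRA preferred-term coding it gives the counting rule: "We will calculate AEs once for a given participant". The display is then set out: "We will present AEs with regards to severity, frequency, relationship, and expectedness". Treatment or period at onset is not among these dimensions. One table is named: "We will present serious AEs leading to premature discontinuation from the study in a table". The paragraph also promises "the proportion of participants who experience at least one AE and the number of AEs per participant", and a comparison of the study's AE rates with published ones.

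Other sections bear on this:

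- Sections 5.1 and 6.2.2: each participant receives four treatments of seven days. Burst, 1 kHz and sham are permuted over the first three periods in six sequences, and 50 Hz is always fourth.
- Section 7.4: relatedness is judged against the study intervention as a whole, not against a waveform. On data capture, "Information to be collected includes event description, time of onset", and "AEs characterized as intermittent require documentation of onset and duration of each episode".
- Section 7.5: AEs are recorded from consent until 7 days (non-serious) or 30 days (serious) after participation ends, with an inquiry at each visit. Visits 3 to 6 each close one treatment period.

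**The concern.** A once-per-participant count is natural in a parallel-group trial, where a participant has one treatment. Here a participant has four, one of them sham. Without a split by treatment at onset, the safety summaries mix sham with active time, and the trial's within-participant control for harms goes unused.

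The mixing matters because the protocol itself expects trouble under sham. Section 6.2.3 names sham as a treatment in which pain relief may be insufficient, and section 7.4 has any deterioration of a participant's condition recorded as an AE. Worsening pain from loss of stimulation would sit in the same count as events caused by active stimulation. Yet section 9.4 makes adverse effects associated with the intervention a reason to stop, and treats differences from published AE rates as important for interpretation. The planned summaries would not show which of the four conditions lay behind either signal. By contrast, section 9.6 lists the primary outcome separately for each type of SCS.

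**Working it through.** The documents state no AE rate or expected AE count, so there is no figure of the plan's own to reproduce. All per-period risks below are assumptions.

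**1. What the pooled summary can show.** Let p_t be the probability of at least one AE under treatment t, independent across periods. The planned proportion with any AE is 1 − Π(1 − p_t), which does not change when rates are swapped between treatments.

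- 20% under sham, 5% under each active treatment: 1 − 0.80 × 0.95³ = 1 − 0.80 × 0.857 = 31.4%.
- 20% under 50 Hz, 5% under each of the others: the same product, again 31.4%.

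The first pattern suggests that withholding stimulation causes the events, the second that 50 Hz does. The pooled proportion cannot tell them apart. With one common risk p it is 1 − (1 − p)⁴: 7.8% at p = 2%, 18.5% at 5%, 34.4% at 10% and 59.0% at 20%, each over all four treatments including sham.

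**2. Whether the data could show it.** Section 7.4 supplies onset time and the dates of each intermittent episode; section 7.5 supplies an inquiry at the end of each period. Each AE can therefore be placed in a period, and the allocated sequence gives the treatment. No new data are needed.

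**3. A conditional case: first occurrence over the whole study, then split by treatment.** With equal, independent risk p in each period, an event is counted in period k only if none occurred before. The counted probability is p(1 − p)^(k−1), a share (1 − p)^(k−1) of the truth.

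- 50 Hz, always k = 4: share (1 − p)³.
- Average of burst, 1 kHz and sham over k = 1 to 3: [1 + (1 − p) + (1 − p)²]/3.

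| p (assumed) | 50 Hz share | Average of other three | Apparent ratio, true ratio 1 |
|---|---|---|---|
| 2% | 0.941 | 0.980 | 0.96 |
| 5% | 0.857 | 0.951 | 0.90 |
| 10% | 0.729 | 0.903 | 0.81 |
| 20% | 0.512 | 0.813 | 0.63 |

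For 25 participants and p = 10%, the expected counts over periods 1 to 4 are 2.50, 2.25, 2.03 and 1.82, against a true 2.50 in each. Counting each participant once within each treatment gives a share of 1 for every treatment. Because recording starts at consent, a pre-treatment event of probability q would multiply every share by (1 − q) without altering the ratio.

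**The case against.** The best case for leaving the plan alone is that safety is not a formal endpoint, the devices are approved and used within labelling, section 7.6 expects no serious side effects or AEs, and 25 participants give only descriptive tables. Section 7.2 also provides an annual list and summary of AEs with reasons for dropout, and sections 7.3 and 7.4 send patterns of unanticipated AEs or SAEs to independent review. All of that stands and limits the weight of the point. None of it is stated to be by treatment, so it does not close the gap.

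Several stronger readings are tempting, and the documents do not support them:

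- **Harms cannot be attributed to a waveform.** They can, from the recorded onset and episode dates. They are simply not attributed in the planned summaries.
- **50 Hz will be undercounted.** As written, section 9.4 produces no 50 Hz count. The undercount needs both a whole-study first-occurrence reading and a split that is not planned. The rule follows directly on preferred-term coding, so once per preferred term is at least as natural a reading. Then only repeats of the same term are lost, the relevant p is smaller and the ratio is nearer 1.
- **The counting rule contradicts the number of AEs per participant.** It does if *once* covers the whole study, but not if it means once per preferred term. The wording is ambiguous; a contradiction is not established.
- **SAEs that do not lead to discontinuation, and non-serious AEs that do, go unreported.** The text names one table but does not say it is the only one, and the general AE presentation is not limited to serious events.
- **Comparison with published rates is invalid.** The documents do not say whether those rates include sham periods, so neither the pooled rate nor the active-only rate can be called the right match.

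**Conclusion.** The point holds as a gap in the planned analysis. Followed as written, section 9.4 would pool sham and active events and would not show harms by waveform or against sham, although the data to do so are collected. This conclusion rests on the text alone and needs no assumed rate.

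The size of any distortion is not determinable from the documents. The ratios of 0.96 to 0.63 are conditional on a particular reading of *once*, on a later split by treatment, and on equal, independent risks of 2% to 20% per period. For rare events the effect is small. With no formal safety endpoint and 25 participants, the change is worthwhile rather than critical. Even with it, 50 Hz stays confounded with the last period, and attribution near a switch stays uncertain because periods run back to back and no washout is described.

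**What to change.** In section 9.4:

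1. Assign each AE to the treatment in force at onset. Add separate categories for pre-treatment events, post-treatment events and procedure-related events (QST, CT, programming). The last category matters because testing and reprogramming share the switch visit.
2. For each of burst, 1 kHz, sham and 50 Hz, show the number exposed, the participants with at least one AE (once per preferred term per treatment) and the number of events. Count a recurrence under a later treatment for that later treatment. The number exposed is needed because section 9.2 allows for 20% attrition (25 × 0.80 = 20), which would fall most heavily on the last period.
3. List all SAEs, and all AEs leading to discontinuation or to return to clinical settings, by treatment.
4. Show active and sham rates separately when comparing with published rates.
5. State that the tables are descriptive, that 50 Hz is confounded with period, and that attribution near switches is uncertain.

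No new data collection is needed. The cost is the assignment rules and a few table shells, and the counts per treatment will be small.

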7.4 Reporting Procedures

Severity of event: We will grade the signs and symptoms as mild, moderate, severe, or life threatening according to the following definitions:

Grade	Definition
Mild	Causing no limitation of usual activity
Moderate	Causing some limitations of usual activities
Severe	Causing inability to carry out usual activities
Life Threatening	Patient was at immediate risk of death from the event

Relationship to study intervention: All adverse events (AEs) must have their relationship to study intervention assessed by the clinician who examines and evaluates the participant based on temporal relationship and his/her clinical judgment. The degree of certainty about causality will be graded using the categories below.

- **Related** – The AE is known to occur with the study intervention, there is a reasonable possibility that the study intervention caused the AE, or there is a temporal relationship

between the study intervention and event. Reasonable possibility means that there is evidence to suggest a causal relationship between the study intervention and the AE.

- **Not Related** – There is not a reasonable possibility that the administration of the study intervention caused the event, there is no temporal relationship between the study intervention and event onset, or an alternate etiology has been established.

Expectedness: The study Principal Investigator (PI) will be responsible for determining whether an adverse event (AE) is expected or unexpected. An AE will be considered unexpected if the nature, severity, or frequency of the event is not consistent with the risk information previously described for the study intervention.

Time period and frequency for event assessment and follow-up: The occurrence of an adverse event (AE) or serious adverse event (SAE) may come to the attention of study personnel during study visits and interviews of a study participant presenting for medical care, or upon review by a study monitor.

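### Section 9.4 plans no split of adverse events by treatment, so events on Sham are pooled with events on active SCS in the rates compared with published studies

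*Combined protocol and SAP*

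**What the plan says.** The safety paragraph of section 9.4 codes AEs by MedDRA preferred term and then sets the counting rule: "We will calculate AEs once for a given participant". The breakdowns follow: "We will present AEs with regards to severity, frequency, relationship, and expectedness". The summaries are described as "including the proportion of participants who experience at least one AE and the number of AEs per participant". The results are then held against outside data: "We will also determine if the AE rates for this study were consistent with pre-study assumptions derived from AE rates in previously published studies". The section adds that a discrepancy could matter greatly for how the study is interpreted. It also states that no formal safety endpoint will be evaluated.

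Section 7.4 defines what enters these counts. "Any medical condition that is present at the time that the participant is screened will be considered as baseline", but if the participant's "condition deteriorates at any time during the study, it will be recorded as an AE". Relationship is graded Related or Not Related to the study intervention as a whole. One ground for Related is that "there is a reasonable possibility that the study intervention caused the AE".

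Under section 5.1 every participant is to receive Burst, 1 kHz, Sham and 50 Hz SCS, each for seven days. I found no split of AEs by treatment or period in sections 7.2 to 7.6 or 9.4.

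**The concern.** In a crossover with a sham period, a participant-level AE count mixes exposures that the design was built to separate. Sham is not a neutral contributor here. Participants are already receiving SCS as clinical care (section 4.1) and have clinically effective settings to which they return at Visit 6 (section 6.2). Sham takes stimulation to zero or to minimal values (section 5.1), and section 6.2.3 foresees inadequate relief during some allocations, naming Sham as the example. Read with section 7.4, pain that becomes worse than at screening during Sham is an AE.

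A high overall rate could therefore reflect loss of therapy and be read as harm from active stimulation. The check against published rates, which section 7.2 repeats for the Annual Report, could not tell the two apart. Nor could the first stopping criterion in 9.4, which asks whether the intervention is associated with adverse effects. Section 3 gives quantifying the effect of sham as a purpose of the design, yet no AE contrast between active and Sham is planned.

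**Working it through.** The plan states no AE rate, so there is no figure to reproduce. The check has two parts.

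**Does any planned output separate the treatments?**

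- Severity, frequency and expectedness do not refer to treatment.
- Relationship does not identify the waveform, or whether the setting was Sham.
- The proportion with at least one AE covers all periods.
- The number of AEs per participant also covers all periods.
- If the counting rule means once per preferred term, which is plausible because it directly follows the coding sentence, the same event on Sham and on Burst in one participant is still one entry.

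None of them does.

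**How much can pooling hide?** All rates here are assumptions. Let a be the proportion with an AE in the three active periods combined and s the proportion with an AE on Sham. Events before treatment or after Visit 6 are ignored. If the two are independent, pooled = 1 − (1 − a)(1 − s). Without independence, pooled lies between max(a, s) and min(1, a + s). With a = 20% (5 of 25):

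| s | Pooled, independent | Of 25 | Range without independence |
|---|---|---|---|
| 0% | 1 − 0.80 × 1.00 = 20% | 5 | 20% |
| 10% | 1 − 0.80 × 0.90 = 28% | 7 | 20–30% |
| 20% | 1 − 0.80 × 0.80 = 36% | 9 | 20–40% |
| 40% | 1 − 0.80 × 0.60 = 52% | 13 | 40–60% |

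With s = 20%, changing a to 10% gives 1 − 0.90 × 0.80 = 28%, and changing it to 40% gives 1 − 0.60 × 0.80 = 52%.

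In reverse, a reported 9 of 25 (36%) fits a = 0% with s = 36%, a = 36% with s = 0%, and any value of a between. This does not depend on independence. The exact 95% interval for 9/25 is 18.0% to 57.5%, so the pooled figure is itself imprecise.

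The same can be put per seven-day period, with probability ps on Sham and pa on each active treatment: pooled = 1 − (1 − ps)(1 − pa)³. For ps of 5–20% and pa of 5–30%, this runs from 18.5% to 72.6%, and the active periods alone, 1 − (1 − pa)³, from 14.3% to 65.7%. A pooled 40% fits ps = 0% with pa = 15.7%, ps = 20% with pa = 9.1%, or ps = 40% with pa = 0%.

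**The case against.** The strongest reply is that this asks for one more descriptive table in a small mechanistic study of approved devices. Onset time is recorded and AEs are asked about at every visit (section 7.5), so the table could be produced later, and silence does not exclude it. Loss of relief on Sham is in any case measured as an outcome: pain ratings are collected at the end of each period, and section 9.1 plans treatment-level estimates for the VAS. Section 6.2.3 says only that inadequate relief is possible, the risk table in 7.1 does not list it, and how often it would be logged as an AE is unknown. Most of this stands and keeps the stakes low. It does not answer the point that the plan, followed as written, compares pooled rates with published ones.

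Five stronger readings are tempting, and the documents do not support them:

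- A reader might infer that only one AE rate will be reported. Section 9.4 also gives the number of AEs per participant and refers to rates in the plural.
- A reader might infer that a participant already counted on Sham contributes nothing further. That holds only for the proportion with at least one AE. A later event may raise the number per participant, and a different preferred term may still count.
- A reader might infer that the listing of temporal summation by type of SCS in section 9.6 makes the plan inconsistent. That listing concerns the primary outcome, and the same paragraph reports exploratory endpoints in aggregate.
- A reader might infer that the published comparison should use active treatments only. The documents do not say how the published rates were defined, so that restriction could make the match worse.
- A reader might infer that the setting at onset is always the allocated waveform. Section 6.2.3 leaves the programmer with the participant and allows a return to clinical settings. Sensory testing, CT and threshold programming can also cause discomfort that belongs to no waveform.

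**Conclusion.** The point holds as a low-stakes, inexpensive improvement to safety reporting. No planned AE summary is split by treatment, and section 7.4 as worded can make worsening pain on Sham an AE, so the planned rates cannot distinguish loss of therapy from effects of active stimulation. That the count runs across all four treatments is an inference from the participant-level wording, but nothing in the text points the other way.

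The true size is unknown. The figures above rest on assumed rates and show only that the pooled rate leaves the active-period rate undetermined. The primary temporal summation analysis is unaffected.

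**What to change.** Keep the overall summary in section 9.4 and add text along these lines:

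> Each AE will also be assigned to the period in force at onset: before treatment, Burst, 1 kHz, Sham, 50 Hz, or returned to clinical settings/after Visit 6. For each treatment we will report the number and percentage of participants with an AE, counting each participant once per preferred term per period, among all randomised participants in whom that treatment was programmed. AEs arising during sensory testing, CT or programming sessions will be reported separately. Worsening of the underlying pain will have its own line. Overall and active-period rates will both be shown beside the published rates, matched to how each published rate was defined.

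The category for a return to clinical settings is needed because settings may be restored during a period and because section 7.5 continues AE collection for 7 days (30 for serious events) after participation. The separate line for worsening pain should appear in every period, since section 6.2.3 does not confine inadequate relief to Sham.

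The cost is a few sentences, with no new data or visits: "Information to be collected includes event description, time of onset". There are downsides. Counts per period will be small and the table purely descriptive. No washout is described, so an event early in a period may belong to the previous treatment. Because 50 Hz is always last, its rate is mixed with time in study. The table must be kept from the blinded team until data collection ends.

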9.5 Outcomes

9.5.1 Primary Outcome

Temporal Summation (TS). The primary endpoint will be SCS-induced changes in temporal summation (TS). TS refers to an increased perception of pain in response to sequential stimuli of equal physical strength (Fig. 9.1A). It is a quantitative sensory testing (QST) model of neural plasticity and central hyper-excitability that is thought to reflect the progressive increase in neuronal firing of dorsal horn neurons in response to repetitive nociceptive C-fiber stimulation (i.e., windup).⁵⁸ In this assessment, we will use a handheld pointed skin probe to apply fixed-intensity stimuli of 256 mN or 512 mN. The weight of the pointed skin probe (i.e., 256 mN or 512 mN) will be selected based on the sensitivity of the patient's painful and control testing sites. In this paradigm, we will apply a single fixed intensity stimulus (256 mN or 512 mN) using a handheld pointed skin probe perpendicular to the subject's skin for approximately 0.5 seconds. Following a 5-second pause, we will apply a train of 10 identical stimuli (256 mN or 512 mN) with a frequency of 1 Hz within an area of 1 cm².

Immediately following the single stimulus and the train of 10 stimuli, we will ask the subjects to report the pain intensity of the stimulus using a 0-100 NRS. We will conduct this testing paradigm (a single stimulus followed by a train of 10 stimuli) three times with the same 256 mN or 512 mN stimulator, and each cycle will be separated by at least 10 seconds. We will calculate TS scores by subtracting the average pain rating of the single-stimulus trials from the average pain rating of the ten-stimuli trials. If the difference is a positive number, we will conclude that there was pain summation, where larger numbers will indicate increased pain summation or TS. If the difference is zero or a negative number, we will conclude that there was no pain summation or TS. The primary endpoint will be the continuous TS values calculated at the end of each seven-day treatment period. Furthermore, at 15- and 30-seconds following the last train of 10 stimuli, we will ask subjects to rate any residual pain sensation in the testing area using the 0-100 NRS.

[figure not shown]

Figure 9.1. Quantitative sensory testing (QST). (A) Temporal summation (TS), (B) Conditioned pain modulation (CPM), and (C) Vibrometry.

